9.14.6.2 Product Evaluation Scale (PES)

The PES (Appendix 13.2.6) will be administered at 180 minutes (i.e., 60 minutes into *ad lib* session) relative to the first puff of the cigarette/ENDS at that visit at Visits 2 to 7.

9.14.6.3 Product Liking Questionnaire

The Product Liking questionnaire (Appendix 13.2.3) will be completed at approximately 180 minutes (i.e., 60 minutes into *ad lib* session) relative to the first puff of the cigarette/ENDS at that visit at Visits 2 to 7.

9.14.6.4 Intent to Use Product Again Questionnaire

The Intent to Use Product Again questionnaire (Appendix 13.2.5) will be completed at approximately 180 minutes (i.e., 60 minutes into *ad lib* session) relative to the first puff of the cigarette/ENDS at that visit at Visits 2 to 7.

9.15 Safety Assessments

Safety assessments in addition to those below may be obtained as necessary at the discretion of the investigator. In the case of an early subject withdrawal, discharge safety assessments should be collected to the extent possible.

9.15.1 Adverse Events

An AE is any untoward medical occurrence associated with the use of the study product, whether or not considered study product-related. An AE can therefore be any unfavorable and unintended sign (including an abnormal laboratory finding), symptom, or disease temporally associated with the use of a study product, whether or not related to the study product.

9.15.1.1 Adverse Event Monitoring

The subjects will be instructed to inform the investigator or staff of any AEs and intercurrent illnesses experienced during the study. Additionally, a specific inquiry regarding AEs will be conducted prior to each product use and at discharge (or upon early withdrawal). The inquiry will be posed in a non-specific manner using open-ended questions so as not to bias the response (e.g., How are you feeling today?).

A subject who has any clinically significant AE or clinically significant abnormal laboratory test value will be evaluated by the investigator or other qualified individual and will be treated and/or followed up until the symptoms or values return to normal or acceptable levels (as appropriate in the opinion of the investigator), or until the subject is lost to follow-up. When appropriate, medical tests and examinations will be performed to document resolution of the event(s).

9.15.1.2 Reporting

All AEs occurring during this clinical trial after the subject has used the first study product will be recorded on the CRF, including the date and time of onset, action taken, outcome (resolved, improved, unchanged, worse, fatal, or unknown/lost to follow-up), duration, relationship to product use, and severity for each event.

Events captured between Screening and the first study product use will be documented as baseline signs and symptoms.

The investigator will review each event and assess its relationship to product use as unrelated, unlikely, possibly, probably, or likely.

In addition, each sign or symptom reported will be graded on a 3-point severity scale using mild, moderate, or severe.

9.15.1.3 Serious Adverse Events

A serious adverse event (SAE) is any AE that in the view of either the investigator (or designee) or sponsor, results in any of the following outcomes: death, a life-threatening AE, inpatient hospitalization or prolongation of existing hospitalization, a persistent or significant incapacity or substantial disruption of the ability to conduct normal life functions, or a congenital anomaly/birth defect. Important medical events that may not result in death, be life threatening, or require hospitalization may be considered serious when, based upon appropriate medical judgment, they may jeopardize the subject and may require medical or surgical intervention to prevent one of the outcomes listed in the above definition.

Life threatening is defined as an AE that in the view of the investigator (or designee) or sponsor, its occurrence places the subject at immediate risk of death. It does not include an AE that, had it occurred in a more severe form, might have caused death.

Unexpected is defined as an AE that is not consistent with the known risk information associated with the study product.

All SAEs, whether or not considered study-related, must be reported by telephone and by fax or e-mail to the sponsor within 24 hours of the site's learning of the SAE or, at the latest, on the following workday. The sponsor's representative to contact about this study is provided in the list of study contacts. The investigator must also inform the IRB, in compliance with GCP reporting guidelines, and the site monitor of any SAE.

9.15.2 Pregnancy

A pregnancy occurring in a female study subject during the study will be documented in the clinical conduct study report to the IRB. Pregnancy itself is not an AE. The investigator or designee will discontinue the pregnant subject from the study and will advise her to seek prenatal care and counseling from her primary care provider. Advice given will be documented in the subject's source document.

The site staff will request the pregnant subject to notify the site of the outcome of the pregnancy (i.e., birth, loss, or termination). To help ensure this, the site staff will follow up with the subject until the end of pregnancy, if in compliance with the site's standard operating procedures (SOPs) and with the subject's consent. This request and the subject's response will be documented in the subject's source document.

9.15.3 Smoking Cessation Information

At Screening and prior to discharge from the study (or upon early termination) all subjects will be advised that, to reduce the health effects of smoking, the best thing to do is to quit and

will be encouraged to contact a qualified medical professional for advice on smoking cessation.

9.16 Blood Sample Collection

Blood sampling will include 2x10 mL and 2x5 mL blood draws during Visit 1 for clinical laboratory assessments and 16x5 mL PK blood draws (4 mL to fill the vacutainer, 1 mL wasted to assure proper blood flow and to clear residual blood and saline from the extension tube connected between the catheter the vacutainer tube) at Visits 2 to 7. Therefore, total blood draw volume is expected to be 510 mL for each subject during the study.

10. DATA ANALYSIS

A brief description of the statistical analysis is included below, detailed methodology for all summary and statistical analyses of the data collected in this trial will be documented in a statistical analysis plan (SAP) prepared by LA Clinical Trials, LLC and agreed upon by the sponsor. The SAP may modify the plans outlined in the protocol; however, any major modifications of the primary endpoints and/or their analysis will also be reflected in a protocol amendment. If deemed appropriate, additional statistical analyses other than those described in this section may be performed and included in the SAP.

10.1 Sample Size Estimation

Since this study is the first to examine the nicotine PK in subjects using all of these blu disposable e-cigarettes, no formal power calculations will be performed. The sample size is typical of other studies reported in literature examining the PK and subjective effects of different tobacco/nicotine products. A sample size of 20 subjects has been determined adequate to meet the study objectives.

10.2 Analysis Populations

10.2.1 Safety Population

The Safety Population will include all subjects who have successfully completed eligibility requirements and using at least one study product.

10.2.2 Outcomes Population

The Outcomes Population is a subset of the Safety Population and will consist of subjects who use a study product and have evaluable PK, subjective effects, or topography data. This population will be used in the summary and analysis of PK, subjective effects, topography, and product use.

10.2.3 Pharmacokinetic Subpopulation

The PK Subpopulation is a subset of the Outcomes Population and will consist of subjects who appear to have met the pre-exposure smoking abstinence period. Upon review of the bioanalytical data, subjects with baseline nicotine levels that are higher than their 120-minute values will be considered as not meeting the pre-exposure smoking abstinence criteria and will be considered for exclusion from the PK Subpopulation. Subjects who have this evidence of not meeting the abstinence criteria in $\geq 50\%$ of their visits will be excluded from the PK Subpopulation.

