3. SUMMARY OF STUDY DESIGN

3.1 Design and Procedures

This will be a part-randomized, open-label abuse liability assessment (ALA) and puffing topography study of nicotine-containing products carried out in 20 healthy adult volunteers who smoke combustible cigarettes.

Subjects will be queried for symptoms of COVID-19 at each encounter (both in person and during telephone reminder calls for visits) (Section 13.1). In addition, at each study site visit, body temperature will be assessed before allowing the subject to enter the clinic.

Subjects will attend the study site for a Screening Visit (Visit 1) within 14 days of entry into the study. At this visit, following informed consent, subjects will complete a nicotine use history questionnaire and also undergo a brief, observed trial use session with one of the blu disposable e-cigarettes they will use during the study. A nasal swab will be used to collect a sample of mucus that will be used to test for a COVID-19 antigen. Blood and urine samples for laboratory assessments will be collected, and an alcohol breath test will be conducted. Medical history will be reviewed, exhaled carbon monoxide (eCO) will be measured, an ECG will be conducted, and vital signs will be assessed. Those who satisfy the inclusion/exclusion criteria will be entered into the study.

Subjects will attend the study site 6 times (Visits 2-7) during the main study for ALA and puff topography assessments. Prior to each visit, subjects will be required to refrain from using any nicotine-containing products for a period of at least 12 hours before study product use.

During their second visit (Visit 2), the subjects will smoke their usual brand cigarette during 2 use sessions. In the first session, subjects will smoke a single combustible cigarette of their usual brand by taking 10 puffs, 30 seconds apart. Blood samples (5 mL) will be obtained for plasma nicotine analysis at -5, 3, 5, 7, 10, 15, 20, 30, 45, 60, 90, and 120 minutes relative to the first puff on the cigarette. Blood pressure and heart rate will be recorded at -10 (baseline), 8, 60, and 120 minutes. Subjects will be asked to complete several subjective effects questionnaires at various points either before, during, or after product use.

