5.2 Replacement of Subjects

The study aims to have 20 subjects complete all 6 study visits (Visits 2-7). Twenty of the subjects who have qualified at Screening will be scheduled to attend Visit 2. An additional 2 qualified subjects will be designated as alternates. They will also attend Visit 2 but will only be randomized if any of the original 20 subjects do not complete Visit 2. After Visit 2, subjects who drop out or are withdrawn may be replaced at the discretion of sponsor.

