### **5.3. Pharmacokinetic Subpopulation**

The PK Subpopulation is a subset of the Outcomes Population and will consist of subjects who appear to have met the pre-exposure smoking abstinence period (Section 8.9.2).

The PK Subpopulation will be used in the summary of PK parameters.

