### **8.9.2. Elevated Baseline**

Upon review of the bioanalytical data, subjects with baseline nicotine levels that are higher than their 120-minute values will be considered as not meeting the pre-exposure smoking abstinence criteria and will be considered for exclusion from the PK Subpopulation. Subjects who do not meet the abstinence criteria in  $\geq 50\%$  of their visits will be excluded from the PK Subpopulation.

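### Abstinence is checked visit by visit, but the PK Subpopulation excludes by subject, so failed visits can stay in the PK summaries or passing visits are lost with them

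*Protocol*

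**What the plan says.** Protocol 3.1 states: "Subjects will attend the study site 6 times (Visits 2-7) during the main study". Each visit tests one product: the usual-brand cigarette at Visit 2 and one e-cigarette at each of Visits 3 to 7. Protocol 4.1.2 and 4.3.2 require a fresh 12-hour abstinence before each visit. Protocol 10.3.1 and SAP 8.9.3 subtract that day's own baseline from that day's concentrations.

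The failure signal is in Protocol 10.2.3: "subjects with baseline nicotine levels that are higher than their 120-minute values will be considered as not meeting the pre-exposure smoking abstinence criteria". SAP 8.9.2 repeats it. Two consequences follow, both for the subject:

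- A subject with the signal "will be considered for exclusion from the PK Subpopulation". Neither document gives a criterion for that decision, and it is taken when the bioanalytical data are reviewed.
- Exclusion is mandatory above a threshold. The Protocol applies it to "Subjects who have this evidence of not meeting the abstinence criteria in" at least 50% of their visits. The SAP wording is "Subjects who do not meet the abstinence criteria in" at least 50% of their visits.

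SAP 5.3 says that the set "will consist of subjects who appear to have met the pre-exposure smoking abstinence period", and gives its use: "The PK Subpopulation will be used in the summary of PK parameters". No section drops or flags a single failed visit, and SAP 8.1 lists excluded subjects only.

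The ANOVA with Dunnett comparisons on Cmax,0-120 and AUC0-120 is run on the Outcomes Population (Protocol 10.3.1, SAP 8.9), which has no abstinence exclusion. Protocol 10.2.2 and SAP 5.2 also assign the summary of PK to the Outcomes Population.

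**The concern.** The abstinence period, the -5 minute sample, the baseline subtraction and the product all belong to a visit. The 50% rule concedes this, because it counts failed visits. Yet the only available action is to keep or drop the whole subject. A set meant to give PK summaries free of non-abstinent visits therefore cannot remove one such visit without also removing that subject's passing visits.

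For subjects below the threshold, the outcome rests on judgement with no stated criterion, made once the concentrations are known in an open-label study.

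The summaries carry weight. Protocol 2.2 names eleven PK parameters as primary endpoints (nine single parameters and two ratios), and only two are tested. For the other nine, the descriptive parameter summary is the only planned result.

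**Working it through.** **1. Threshold.** The smallest number of failures that forces exclusion is 50% of the visits attended, rounded up. For six visits it is 3. For subjects with fewer visits it is 3 of 5, 2 of 4, 2 of 3, 1 of 2 and 1 of 1.

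**2. What the rule does to a completer.** This step needs no failure rate.

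| Failed visits of 6 | Exclusion | If kept: failed visits in the summaries | If excluded: passing visits lost |
|---|---|---|---|
| 1 | discretionary | 1 | 5 |
| 2 | discretionary | 2 | 4 |
| 3 | mandatory | n/a | 3 |
| 4 | mandatory | n/a | 2 |
| 5 | mandatory | n/a | 1 |
| 6 | mandatory | n/a | 0 |

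**3. What a kept failed visit contributes.** Failure means C(-5) > C(120), so the adjusted value C(120) - C(-5) is negative. That time point closes AUC0-120 and opens AUC120-180, so it enters both Cavg values and their ratio. Neither document says how negative adjusted values are handled.

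**4. Possible size, independent failures.** Inputs from the documents: 20 completers (Protocol 5.2) with 6 visits each, so 120 visits. Assumption: each visit fails independently with probability p. No rate is given, so a range is shown. Let K be the number of failures per subject, K ~ Binomial(6, p).

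- Failed visits expected = 120p.
- *All subjects with 1-2 failures kept:* failed visits kept = 20 × [P(1) + 2P(2)]; passing visits lost = 20 × [3P(3) + 2P(4) + P(5)].
- *All subjects with 1-2 failures excluded:* failed visits kept = 0; passing visits lost = 6 × 20 × [1 - (1-p)^6] - 120p.

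At p = 0.10, P(1) = 0.3543, P(2) = 0.0984, P(3) = 0.01458, P(4) = 0.001215 and P(5) = 0.000054. Failed visits kept = 20 × (0.3543 + 0.1968) = 11.0 of 12, or 91.9%. Passing visits lost = 20 × (0.04374 + 0.00243 + 0.00005) = 0.9. If all subjects with 1-2 failures are excluded, passing visits lost = 120 × (1 - 0.5314) - 12 = 44.2 of 108.

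| p | Failed | Failed kept (1-2 kept) | Share kept | Passing lost (1-2 kept) | Passing lost (1-2 excluded) |
|---|---|---|---|---|---|
| 0.05 | 6 | 5.9 | 97.7% | 0.1 | 25.8 of 114 |
| 0.10 | 12 | 11.0 | 91.9% | 0.9 | 44.2 of 108 |
| 0.20 | 24 | 17.7 | 73.7% | 5.6 | 64.5 of 96 |

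With subjects with 1-2 failures kept, the share kept is 52.8% at p = 0.30 and 42.8% at p = 0.35. It crosses one half at p = 0.314.

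**5. Clustered failures.** The binomial is replaced by a beta-binomial with within-subject correlation rho (also assumed), again with subjects with 1-2 failures kept. At p = 0.10:

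| rho | 0 | 0.1 | 0.2 | 0.3 | 0.5 |
|---|---|---|---|---|---|
| Share of failed visits kept | 91.9% | 74.3% | 59.1% | 46.7% | 27.9% |
| Passing visits lost | 0.9 | 2.5 | 3.4 | 3.7 | 3.4 |

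The rate at which the share crosses one half falls to 0.251, 0.171 and 0.067 for rho = 0.1, 0.2 and 0.3. At rho = 0.5 the share was below one half at every rate computed.

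**6. Whether the present marker can serve at visit level.** Assume linear kinetics and the same curve shape for all products. Let B be the baseline, f the fraction of it remaining at 120 minutes, R the cigarette's own contribution at 120 minutes and d the product's delivery relative to the cigarette. A visit fails when B > fB + dR, that is, when B > dR/(1 - f). The tolerated baseline is proportional to d. Protocol 1.1 cites e-cigarette Cmax from 25% to near 100% of a cigarette's. At d = 0.25, a visit fails at a quarter of the baseline that a cigarette visit tolerates.

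**The case against.** A reader might infer that most failed visits remain in the PK summaries. The documents do not support that. It needs a low failure rate, near-independent failures, and every subject with one or two failures kept. No rate is given. Non-abstinence is behaviour that may well recur in the same subject. The plan also says that such subjects are considered for exclusion. Steps 4 and 5 show the share falling below one half under other plausible inputs.

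A reader might also infer that the hypothesis tests are contaminated by this rule. They are run on the Outcomes Population, so changing the PK Subpopulation alters no test.

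The strongest objection is to the obvious remedy. Dropping every visit that fails the present marker would selectively remove low-uptake e-cigarette visits, because the 120-minute value depends on what the product delivered (step 6). That would tend to raise those products' mean Cmax and AUC. Excluding whole subjects at least keeps each subject's set of products intact. This stands: a visit-level rule is safe only with a check that does not use post-exposure data, and no rule can promise to lose no valid visit.

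Three further defences carry less weight.

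- Treating a subject who fails half the visits as generally non-compliant is defensible, but it does not justify keeping failed visits from other subjects.
- The exhaled CO check at each visit (Protocol 4.1.2) is a visit-level gate, but the plan itself adds a nicotine-based check after it.
- Any nicotine-based check needs the bioanalytical data, so the complaint about timing applies only to the discretionary clause.

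It is also fair to say that parameters and excluded subjects are listed, so failed visits could be traced, and that no bias in Cmax or AUC has been quantified here.

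**Conclusion.** The mismatch of unit is real and follows from the rule itself at any failure rate or clustering. For a completer with one or two failed visits, neither available decision is right: either one or two failed visits stay, each with a negative adjusted 120-minute value, or five or four passing visits are lost. With three to five failures, exclusion is mandatory and costs three to one passing visits. The threshold of three applies only to subjects with six visits.

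The total effect cannot be read from the documents. With subjects with one or two failures kept and failures independent, about 98%, 92% and 74% of failed visits would stay at assumed rates of 5%, 10% and 20%. With strong clustering (46.7% at a 10% rate and a correlation of 0.3), or with rates above about 31%, fewer than half would stay.

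The reach is limited to the PK parameter summaries. It is worth correcting because those summaries are the only planned result for nine of the eleven PK endpoints in the Protocol, and because the discretion is open-ended.

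**What to change.** In Protocol 10.2.3 and SAP 5.3 and 8.9.2:

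- Define the PK Subpopulation as a set of subject-visits. Exclude only the visits that fail the abstinence check, and keep the subject's other visits.
- Delete the 50% rule and the clause on considering subjects for exclusion.
- Base the check on a criterion that uses only the -5 minute value and is fixed before the concentrations are seen. Drop the comparison with the 120-minute value.
- In SAP 8.1, list excluded visits by product.
- Show the PK summary for the Outcomes Population alongside. This also settles which set Protocol 10.2.2 and SAP 5.2 and 5.3 intend for the PK summaries.

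The change is to wording and output only, with no new data. Protocol section 10 asks for an amendment when a major change affects the analysis of primary endpoints, so the sponsor should decide whether this change qualifies. The numbers of subjects will differ between products in the PK Subpopulation summaries; Protocol 10.3 and SAP 7.3.1 already accept reduced denominators. Some visits may still be misclassified, which is why both summaries should be shown.

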10.3 Data Analysis, Summarization, and Statistical Methods

SAS software (version 9.3 or higher, Cary, NC) will be used for all data presentation and summarization including summary tables, graphs, and data listings, except as noted in 10.3.1. In general, all data will be listed by subject and time point and summarized by study product and time point using descriptive statistics appropriate for the endpoint. Figures will be used to display the data graphically.

Missing data will not be imputed. Where individual data points are missing because of dropouts or other reasons, the data will be considered missing at random and summarized based on reduced denominators.

10.3.1 Nicotine Pharmacokinetic Analysis

Individual nicotine concentrations will be adjusted for baseline nicotine (“baseline-adjusted”) and all PK parameters will be calculated based on the adjusted concentrations. Baseline adjustment will be performed by subtraction of the baseline nicotine concentration from each nicotine concentration obtained after test product use on that day for each subject.

Pharmacokinetic parameters of plasma nicotine levels will be calculated using noncompartmental methods with the Phoenix WinNonlin version 8 software platform (Certara, Princeton, NJ). Plasma concentrations and the computed plasma PK parameters will be listed for each study product and subject.

Plasma nicotine levels will be plotted as mean concentration in relation to time, with 95% confidence intervals of the mean for each product at each time point.

The following PK parameters will be calculated; all parameters will be baseline-adjusted using the value at time -5 minutes:

- $C_{max,0-120}$ = Maximum plasma concentration during defined use session
- $T_{max,0-120}$ = Time of maximum plasma concentration during defined use session
- AUC_{0-120} = Area under the plasma concentration-time curve from time 0 to 120 minutes during defined use session
- $Cavg_{0-120}$ = Average concentration from 0 to 120 minutes defined as $AUC_{0-120}/120$ minutes.
- $C_{max,120-180}$ = Maximum plasma concentration during the *ad libitum* puffing session
- $T_{max,120-180}$ = Time of maximum plasma concentration during the *ad libitum* puffing session
- $AUC_{120-180}$ = Area under the plasma concentration-time curve from time 120 minutes to 180 minutes during the *ad libitum* puffing session
- $Cavg_{120-180}$ = Average concentration from 120 to 180 minutes defined as $AUC_{120-180}/60$ minutes.
- AUC_{0-180} = Area under the plasma concentration-time curve from time 0 minutes to 180 minutes during both puffing sessions
- Ratio of $C_{max,120-180}/C_{max,0-120}$ = ratio of these two parameters
- Ratio of $Cavg_{120-180}/Cavg_{0-120}$ = ratio of these two parameters

Plasma concentrations below the limit of quantitation will be set to one-half of the lower limit of quantitation for the calculation of descriptive statistics of unadjusted plasma nicotine concentrations and for the calculation of baseline-adjusted nicotine concentrations.

Nicotine concentrations and PK parameters will be listed by subject and summarized by study product using descriptive statistics.

A one-way or repeated measures analysis of variance will be conducted on the Outcomes Population Cmax₀₋₁₂₀ and AUC₀₋₁₂₀ to assess for statistical differences between the Usual Brand combustible cigarette and the blu disposable e-cigarettes. Significance based on a Dunnett's multiple comparison assessment will be reported.

